Protocol Title: Family-Centered Cesarean: A Randomized Controlled Trial
Protocol Version: 11
Protocol Date: 3/15/2019
Locations: Aurora Sinai Medical Center, Milwaukee, Wisconsin
Aurora BayCare Medical Center, Green Bay, Wisconsin

I. BACKGROUND AND SIGNIFICANCE

Cesarean sections are one of the most common surgical procedures performed world-wide. They are performed for both maternal and neonatal indications. Today, cesarean sections account for 20% of all births globally.¹ From 1996-2009, the rates of cesarean sections in the United States rose approximately 60%; these rates have remained unchanged since 2010. The national rate of cesarean deliveries in 2012 was 32.8%.²

As the number of cesarean sections increase and vaginal deliveries decrease, women report that they are less satisfied with their overall child birthing experience.^{1, 3-6} Mother and partner experiences differ between cesarean and vaginal delivery; the biggest difference is that, during vaginal delivery, the newborn is more often directly given to mom immediately after birth, which initiates early mother-newborn interactions through skin-to-skin contact and breastfeeding. Additionally, a mother and her support people are able to see their child enter the world without a barrier between them. Cesarean sections create a delay in the mother-newborn interaction, as the newborn is routinely separated from the mother. Such separation leads to later skin-to-skin contact and makes it harder for mothers to initiate breastfeeding.^{1, 4} This separation also leads to greater dissatisfaction with the birthing process and a mother is more likely to feel she was unable to participate in the birth of her child.³

To improve the overall child birthing experience, the family-centered/gentle cesarean delivery method mimics a vaginal birthing experience. Similar to a vaginal delivery, a mother can watch the birth, and the newborn is immediately placed on the mother's chest following cesarean delivery. Studies have shown that immediate mother-newborn interactions and skin-to-skin contact is advantageous in promoting the bond between mother and newborn, breastfeeding, and overall patient satisfaction with the birthing process.^{1, 5} The family-centered/gentle cesarean method is relatively new. Limited information is available in regards to differences in maternal and neonatal outcomes when comparing traditional cesarean methods to that of the family-centered/gentle cesarean. Additionally, available information often refers to this methodology as either family-centered cesarean or gentle cesarean; we will refer to this method as the family-centered cesarean from here on out.

One European study conducted in Germany compared family-centered and traditional cesarean delivery methods, and determined that no additional complications arose for mother or newborn when using the family-centered cesarean method.⁶ Although the Memorial Hospital of Rhode Island has implemented the family-centered cesarean method as the standard of care during cesarean delivery, to our knowledge, no studies have been conducted in the United States that compare the family-centered cesarean method to traditional methods of cesarean delivery.⁴ Magee et al. further supports that the techniques used in their hospital have not been evaluated and that the hospital's approach to family-centered cesarean deliveries should be further examined as it relates to maternal and neonatal outcomes, as well as overall patient satisfaction.⁴

The purpose of this study is to determine if patient birthing experiences differ between the family-centered and traditional cesarean methods. We hypothesize that the family-centered cesarean method will lead to more unique and personalized cesarean birthing experiences without increasing the risks of adverse neonatal and maternal outcomes from those documented

with the traditional cesarean.

II. SPECIFIC AIMS

Primary Objective

The primary objective of this study is to compare patient satisfaction of the family-centered cesarean birthing experience with that of the traditional cesarean experience.

Secondary Objective

The secondary objective of this study is to determine if skin-to-skin contact (i.e., family bond initiation) occurs earlier and in-hospital breastfeeding initiation is more likely with the family-centered cesarean delivery method than traditional cesarean delivery method.

Tertiary Objective

The tertiary objective of this study is to determine if differences in maternal and neonatal outcomes exist between cesarean delivery methods (family-centered versus traditional cesarean).

III. STUDY DESIGN

Subject Enrollment

[figure not shown]
Women undergoing a scheduled cesarean delivery at ≥ 38 weeks of gestation who present at Aurora Sinai Medical Center and Aurora BayCare Medical Center and have their babies delivered by obstetrics and gynecology physicians during June 1, 2016 through May 31, 2019 will be enrolled in this study. Patients who meet the study criteria will be recruited via obstetrics and gynecology physicians on the day of their scheduled cesarean section. Patients who agree to participate in this study will be formally consented. The study will be described to the patient using the following script, containing objective language so as to minimize bias or influence when the patient is later asked to identify her preference of the 2 cesarean delivery methods. Note that Method 1 below describes the family-centered delivery method, while Method 2 describes the traditional delivery method.

“We are conducting a patient satisfaction study on two methods of cesarean section. Both of these methods are used throughout the United States, and neither has been proven to be better than the other. Method 1 involves lowering part of the surgical drape exposing a transparent window through which you can watch the birth of your baby; the baby will be placed on your chest immediately after the delivery. Cleaning and evaluation of your baby will be done by a nurse who is standing next to you at the head of the bed. Method 2 involves keeping the surgical drape up throughout the entire surgery so that the birthing process will not be visible, and your baby will be taken to the warmer to be evaluated and cleaned after birth but is available to be laid on your chest at any point upon request.”

Randomization to Method

Eligible patients will be formally consented on the day of their scheduled cesarean sections by the research coordinator, resident physician(s), charge nurse or nurse. Following enrollment, each patient will be asked to state which method of cesarean delivery she would prefer, if given the option to choose. Preference represents a potential factor influencing patient satisfaction that will be later incorporated into the statistical analysis, based on a 2 x 2 factorial (Method x Preference) design. Documentation of preference at this time (versus following random assignment to cesarean delivery method) is important for minimizing the bias or influence of the random assignment upon the patient’s declared preference.

The patient will be randomized to 1 of the 2 delivery methods by the research coordinator, resident physician(s), charge nurse or nurse, who will present the patient with a sealed envelope. The envelope will contain a slip of paper identifying the patient’s random assignment to either the family-centered cesarean delivery method (Method 1) or the traditional delivery method (Method 2). Fifty percent of all envelopes preassembled for patients will contain paper slips stating “Family-centered”, while the remaining 50% will contain slips stating “Traditional,” allowing for a 1:1 allocation of delivery methods.

Assessment of patient satisfaction following delivery

The primary objective of this study is to compare levels of patient satisfaction with the birthing experience between the two cesarean delivery methods. To assess patient satisfaction, each patient will be verbally surveyed by the study coordinator using an 11-item questionnaire. Similar to the questionnaire used by Armbrust and his colleagues⁶, items on our questionnaire will relate specifically to the mother's birthing experience and answers available per item will be in the form of a modified Likert scale, ranging from 1, the lowest level of agreement or degree of satisfaction, to 5, the highest level of agreement or degree of satisfaction. The survey questions will be asked before discharge (approximately within 48 hours after the delivery), to allow sufficient opportunity for the mother and newborn to bond before discharge.

IV. STUDY POPULATION

Pregnant patients who plan to deliver at Aurora Sinai Medical Center (ASMC) and Aurora BayCare Medical Center (ABMC) will be enrolled in this study. ASMC is a 177-bed, urban community-based hospital located in Milwaukee, Wisconsin. In 2014, 2,479 deliveries were performed at this facility with 26.4% of births delivered via cesarean sections. ABMC is a 167-bed, urban community-based hospital, located in Green Bay, Wisconsin. In 2014, 1,623 deliveries were performed at this facility with 26.4% of births delivered via cesarean section. These numbers reflect all cesarean deliveries, but do not necessarily reflect deliveries that are planned, which may total less than ½ of all cesarean deliveries.

Inclusion

- Women ≥ 18 years of age
- Women with planned cesarean section
- ≥ 38 weeks of gestation
- Singleton fetus
- Reassuring fetal status (status of scheduled, green and some yellow)

Exclusion

- Women with an urgent or emergency clinical situation in which the medical staff caring for the patient determines that obtaining consent would interfere with the patient's clinical care
- Patients that decline to consent to participate (an opt out log including the consenters initials, time of day, and reason is kept)
- Patients with anticipated heavy intraoperative bleeding (bleeding disorders, placenta previa, suspected placenta abruption, etc.)
- Known maternal co-morbidities that could impact neonatal well-being (e.g., uncontrolled diabetes, etc.)
- Chorioamnionitis or prolonged rupture of membranes (≥ 18 hours in duration)
- Known fetal anomalies
- BMI ≥ 45 kg/m²
- Estimated fetal weight < 2000 grams

V. SAMPLE SIZE

No randomized controlled trials have focused on outcomes associated with the family-centered

cesarean method in the United States. Furthermore, the only randomized controlled trial published in the obstetrics literature was a study conducted in Berlin, Germany by Armbrust and his colleagues, who assessed the eligibility of 250 women with indication for planned cesarean section. From this initial population, 205 total women were randomized to the study groups of Charité (family-centered) cesarean delivery and traditional cesarean delivery.⁶

In our study, a factorial design with 2 design variables (Cesarean Delivery Method [Gentle, Traditional] and Preference of Method [Gentle, Traditional]) will be used. A sample size of 508 total patients (127 patients in each of the 4 Method x Preference combinations) has been determined necessary to detect a 0.5-point difference in mean satisfaction scores (on a 5-point scale) and a 15-minute difference in time-to-initiation of family bond between the 2 groups of each design variable, given 2-factor generalized linear modeling with normally-distributed (or log-transformed) responses, standard deviation of 2 points (for satisfaction score) and 1-hour (for family bond initiation), alpha of 0.05, and power of 0.80. Moreover, to detect a 15% difference in probability of breastfeeding prior to discharge between the 2 groups of each design variable using logistic regression, a sample size of 432 total patients (108 patients in each of the 4 Method x Preference combinations) would be necessary. To detect clinically-relevant differences for all outcomes (responses) of interest in the Primary and Secondary Objectives, we will target 508 total patients.

VI. DESCRIPTION OF DELIVERY METHODS

Method 1: Family-centered cesarean

Standard preoperative preparation will be performed in the patient's room, including surgical site hair clipping, chlorhexidine wash (at ASMC only), IV placement, completion of pre-procedure operating room checklist, and administration of prophylactic antibiotics, antiemetics (at ASMC only), and fluids. The patient will then be taken to the operating room. The pulse oximeter will be placed on the mother, and the electrocardiogram leads will be placed away from anterior chest wall or via an EKG back-patch to allow space for newborn and mom skin contact. Regional spinal anesthesia will be administered in normal fashion. The mother will lie down on the bed and, once sufficient anesthesia block is obtained, her gown will be removed and a blanket will be provided for her to cover her chest, allowing for easier skin-to-skin contact after delivery. Prior to the lowering of the drape, the mother's head will be elevated. Fetal heart tracing will be monitored until adequate block is obtained to confirm fetal well-being.

Preoperative preparation will continue with abdomen preparation. We will then wait 3 minutes from wash to dry before placing the blue drape on the mother's abdomen and attaching it to the IV poles, thereby screening the mother from the first part of the surgery. After the fetal head enters the uterine incision, the opaque layer of the drape will be lowered, exposing a transparent drape layer that will enable the mother and her support person to watch the birth. The drape will only be lowered and the rest of the family-centered technique carried out if no complications occur during the operation. In the event of unexpected complications, such as heavy bleeding or problems with delivery of the newborn's head, the surgical drape will not be lowered. Provided that the technique is continued, the newborn's head, followed by the rest of the body, will be delivered by the surgeon in full view of the mother. The umbilical cord will be clamped and cut by the surgeon, and the newborn will then be handed off to the nurse waiting by the mother's

head. The nurse will be holding a sterile drape to receive the newborn and prevent contamination of the surgeon's hands. The nurse will then immediately place the newborn on the mother's bare chest skin, or be given to the mother's support person, where the newborn will be dried and warmed with fresh towels. The opaque layer the drape will then be raised back up, screening the mother from the remaining surgery.

While on the mother's chest, the newborn's well-being will be initially evaluated by the nurse and respiratory therapist per hospital cesarean section protocol. APGAR scores will be obtained, and the pulse oximeter will be applied to the newborn's right hand. Suctioning needed at that time will be performed using a bulb or mechanical suction. The nurse will remain near the patient's head, as long as needed to ensure maternal and neonatal well-being. Should the mother develop complications that prevent her from being able to comfortably hold the newborn, such as nausea/vomiting, fatigue, or drowsiness from medications, the nurse will be available to help with the newborn. As long as the patient remains stable, the newborn will be laid on mother's chest in a way that allows suckling. The newborn vitamin K administration and erythromycin ointment can be applied per hospital protocol, either while she is holding the newborn or after she is in recovery. The newborn will be weighed following surgery, while the mother is transferred to her bed, unless she requests it be done earlier.

Method 2: Traditional cesarean

Standard preoperative preparation will be performed in the patient's room, including surgical site hair clipping, chlorhexidine wash (at ASMC only), IV placement, completion of pre-procedure operating room checklist, and administration of prophylactic antibiotics, antiemetics (at ASMC only), and fluids. The patient will then be taken to the operating room. The pulse oximeter will be placed on the mother's finger, and electrocardiogram leads will be placed in the usual fashion on the chest. Regional spinal anesthesia will be administered in normal fashion. The mother will lie down on the bed, and fetal heart tracing will be monitored until adequate block is obtained to confirm fetal well-being.

Preoperative preparation will continue with abdomen preparation. We will then wait 3 minutes from wash to dry before placing the blue drape on the mother's abdomen and attaching it to the IV poles, thereby screening the mother from the entire surgery. After delivery, the newborn will be handed off to a nurse waiting at the side of the mother who will take the newborn to the warmer on the opposite side of the operating room. The newborn will be dried and warmed with fresh towels on the warmer, while being evaluated by the nurse and respiratory therapist per hospital cesarean section protocol. The nurse will then proceed with newborn measurements, weight, bath, and administration of vitamin K and erythromycin ointment. The newborn will be swaddled and kept in the warmer until the mom requests that the newborn be brought to her or until the surgery has been completed and the mom is ready to be transferred to the recovery room.

VII. DATA COLLECTION

Patients will be followed throughout their hospital stay. The following variables of interest will be retrospectively collected from EPIC or recorded during the surgery on the OR Worksheet (* - Note, the OR Worksheet was updated on 2/16/2018.):

Maternal Variables of Interest

- Medical record number
- Date of birth
- Delivery Hospital (0=ASMC; 1=ABMC)
- Date of consent for scheduled cesarean section
- Date of procedure
- Calculated maternal age
- Race
- Ethnicity
- Gravidity (Gx)
- Parity (Pxxxx)
- Gestational Age (XwXd)
- Height (inches)
- Weight (lbs)
- Calculated BMI (kg/m²)
- History of previous vaginal delivery (0=No; 1=Yes)
- History of previous cesarean delivery (0=No; 1=Yes)
- Reason for previous cesarean delivery
- History of previous abdominal/pelvic surgery (0=No; 1=Yes)
- Reason for planned cesarean delivery
- Type of cesarean delivery technique (0=Family-centered; 1=Traditional)
- Identified mother preference (0=Family-centered; 1=Traditional)
- Type of cesarean delivery (0=NA; 1=Classical; 2=Low Transverse)
- Type of skin incision (0=NA; 1=Pfannenstiel; 2=vertical)
- Operative start time (00:00:00)
- Operative stop time (00:00:00)
- Duration of operation (minutes)
- Estimated blood loss (mL)
- Hemorrhage EBL >1000mL (0=No; 1=Yes)
- Complications occurred (0=No; 1=Yes)
- Type(s) of complication(s) that occurred
- If the mother's delivery technique was family-centered, was she switched to a traditional cesarean? (0=No; 1=Yes)*
- Was mom offered to view the birth of her baby? (0=No; 1=Yes)*
- If offered to view the birth of her baby, was the drape dropped? (0=No; 1=Yes)*
- Was mom/other support person offered baby right away? (0=No; 1=Yes)*
- Physician Name
- Did family bond occur in the OR? (0=No; 1=Yes)*
- Time from birth to initiation of family bond (minutes)*
- Person who initiated family bond (0=Mother; 1=Father; 2=Other Support Person)*
- Family bond interrupted in the OR (0=No; 1=Yes)*
- Reason family bond interrupted in the OR*
- If the family bond DID NOT occur, why not?*

-
- Surgical site infection associated with this surgery (0=No; 1=Yes)
 - Time to skin-to-skin contact & all other related skin-to-skin variables identified
 - Breastfeeding status flowsheet data (3=Unknown; 2=No; 1=Yes)

Neonatal Variables of Interest

- Birth weight
- 1-min APGAR
- 5-min APGAR
- Documented neonatal infection (0=No, 1=Yes)
- Newborn heart rate at 10 minutes*
- Newborn respiratory rate at 10 minutes*
- Newborn temperature at 10 minutes*
- Time taken for newborn to reach oxygen saturation >90%*

Assessment of patient satisfaction will be conducted following delivery. Questions from an 11-item questionnaire will be asked of the patient by the study coordinator, [name], or one of the resident physicians or the nurses/charge nurses at ASMC and study coordinator, [name], or one of the nurses or charge nurses at ABMC. Please see the questionnaire displayed in a separate document.

Please note, that while we aim to obtain the OR worksheet and patient satisfaction survey from all patients enrolled in the study, there may be circumstances in which one or the other were not completed. If a patient has either the OR worksheet or the patient satisfaction survey completed, we will not exclude them from the study/analyses, but it will be adjusted for.

We will perform interim analyses throughout the study. In order to identify those individuals who may not have been asked to participate within our study or who did not participate within our study (we will not know specifically who declined or who was not asked to participate), we are requesting data from our Quality Teams, within our labor and delivery units, and Research Analytics. Individuals who were classified as scheduled or planned non-emergent (green or yellow) cesarean deliveries will be identified, as planned emergent (those deemed red) cesarean deliveries are not eligible for the study. Additionally, all variables of interest identified above may be requested in addition to variables of interest that would allow us to further determine whether a patient was ever eligible for the study (see study inclusion and exclusion criteria).

Please note, the OR Worksheet and patient satisfaction surveys were updated on 2/16/2018. Based on our interim analyses, we have decided to change the OR worksheet and patient satisfaction surveys to further clarify how we want data to be collected/recorded. Our biostatistician carefully reviewed the changes to make sure that we are acquiring the same information, but in a clearer manner (i.e., there is less room for interpretation). Furthermore, changes on the translated patient satisfaction survey were reviewed by a certified Aurora Translator, who verified that the document was clear/the changes made are appropriate.

VIII. STATISTICAL PLAN

To describe our study population and assess equivalency in characteristics among patients in the 4 Method x Preference combinations, we will compute frequencies, means with 95% confidence intervals, and medians with interquartile ranges, as appropriate per variable type. Differences among the groups will be tested using the Pearson chi-squared test of independence, Student's t-test, or Wilcoxon's rank sum test, respectively. To generally describe the outcomes (responses) corresponding to each of our 3 study objectives, both within and across the 4 Method x Preference combinations, we will again compute frequencies, means with 95% confidence intervals, and medians with interquartile ranges, as appropriate per variable type.

For each outcome of interest, we will also develop a mixed regression model to examine the fixed main and interaction effects of Method and Preference. All models will be structured with appropriate response distributions, likely including the lognormal (normal distribution with natural log-transformed response) for continuous responses (e.g., time, weight, vitals), multinomial for survey questions of satisfaction, and binomial for 2-category outcomes (e.g., breastfeeding). Following back-transformation or exponentiation of parameter estimates, model results will be interpreted, respectively, as the percentage difference between groups, ratio of odds of a lower value, and ratio of odds of an outcome occurring. Unobserved outcome heterogeneity will be captured by the delivering physician nested within hospital, each combination of which will define a separate random variable and model intercept.

IX. POTENTIAL RISKS AND BENEFITS

Risks associated with Method 1 (family-centered cesarean delivery) include unforeseen patient and/or family discomfort with viewing the surgical field. Patients will be made aware of the potential risk of such discomfort prior to consenting to participating in the study. Notably, risks of this nature are a normal component of any cesarean delivery. Therefore, we will discuss the risk of viewing discomfort with all patients regardless of study participation. An additional risk associated with participating in either method could be loss of confidentiality due to obtaining limited protected health information. However, to minimize risk, all data will be stored on a password protected computer.

A potential benefit of our study is that we may be able gather level-1 evidence to support local, regional, and possibly broader use of a novel method of cesarean delivery, currently being explored nationally and internationally. We hypothesize that there will be improved maternal satisfaction using the family-centered method. We also hypothesize that neonatal morbidity will not be increased and benefits may include earlier skin-skin contact and greater likelihood of breastfeeding.

X. REFERENCES

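### Preference is elicited just before a sealed envelope is presented, with no numbering, opening log or independent preparation stated, so re-drawing toward a stated wish is neither prevented nor detectable

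*Combined protocol and SAP*

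**What the plan says.** Section III (Randomization to Method) sets out three steps.

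- Consent: "Eligible patients will be formally consented on the day of their scheduled cesarean sections by the research coordinator, resident physician(s), charge nurse or nurse".
- Preference: "Following enrollment, each patient will be asked to state which method of cesarean delivery she would prefer, if given the option to choose". The section requires this to be documented before random assignment, and explains that the aim is to keep the assignment from influencing the answer.
- Assignment: the same list of roles, ending "charge nurse or nurse, who will present the patient with a sealed envelope".

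The allocation rule is a proportion: "Fifty percent of all envelopes preassembled for patients will contain paper slips stating" the family-centered method, with the other half naming the traditional one.

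Preference is the second design factor, "later incorporated into the statistical analysis, based on a 2 x 2 factorial (Method x Preference) design". Section VIII fits Method, Preference and their interaction as fixed effects, and adds random intercepts: "Unobserved outcome heterogeneity will be captured by the delivering physician nested within hospital". Section V assumes 508 women, 127 in each Method x Preference cell.

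The plan does not state how the sequence is generated, whether envelopes are numbered or opaque, that the next one must be used, who prepares or holds them, whether openings are logged, or whether there are separate series by hospital or preference.

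**The concern.** The plan asks for the fact most likely to tempt someone to depart from the sequence (which method the woman wants) immediately before the step that it could affect. The envelopes are handled by people in clinical and enrolling roles. If a slip disappoints, nothing stated ties the woman to that envelope, and no stated record would show that another had been opened. The one log the plan mentions, the opt-out log in Section IV, covers refusals and not envelopes.

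The primary outcome is the woman's own satisfaction rating, given by a woman who knows which method she had. Women with strong wishes are the ones most likely to be accommodated, and strength of wish plausibly affects the rating. The plan records only which method is preferred, so a selection of this kind would stay in the Method contrast after adjustment.

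**Working it through.** **1. The plan's own sample size.** Inputs from Section V: difference 0.5, SD 2, alpha 0.05 (taken as two-sided), power 0.80. Per group n = 2 x (1.96 + 0.84)² x 2² / 0.5², about 252, so 504 in total. The t-based version gives 252.13, hence 253 per group and 506 in total. Rounded up to four equal cells, this is 4 x 127 = 508. The stated figure reproduces, and power at 254 per group is 0.80.

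**2. What the Preference term removes.** Assume a fraction s of women receive their preferred method whatever the envelope says, a 50/50 preference split, a 0.5-point preference effect and no method effect. The arms then differ in preference share by s, and the unadjusted bias is 0.5 x s. The standard error is 2 x √(2/254) = 0.177.

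| s | Unadjusted bias | Unadjusted type I error | Power for Method, Preference in model |
|---|---|---|---|
| 10% | 0.05 | 0.059 | 0.80 |
| 20% | 0.10 | 0.087 | 0.79 |
| 30% | 0.15 | 0.135 | 0.77 |

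With Preference in the model, as planned, this component of bias disappears at little cost in power.

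**3. What it does not remove.** Take the women who prefer Method 1. Assume that a fraction f = 0.10 of those drawn to Traditional are moved to Method 1, and that their scores differ from the others' by g = 1 to 2 points. Neither figure is in the documents. The Traditional mean shifts by f x g = 0.10 to 0.20, and the Method 1 mean by f x g / (1 + f) = 0.09 to 0.18.

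- If these women score low under Traditional and high under Method 1, both means rise and the contrast changes by only 0.01 to 0.02.
- If they score on the same side of the others under both methods, the shifts add: 0.10 + 0.09 = 0.19, up to 0.20 + 0.18 = 0.38. The sign depends on which side.

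These shifts concern one preference group, not the whole trial. One assumed rate gives anything from almost nothing to a large part of the 0.5-point target, in either direction, so no estimate is defensible.

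**4. Chance imbalance.** With 254 envelopes of each kind and no stratification, a subgroup of m women has a family-centered count with SD √(m x 0.25 x (508 − m)/507). For m = 254 the SD is 5.64 and the 95% range 116 to 138, a between-arm difference in that subgroup's share of ±8.7 points. For m = 102 it is ±7.0 points. The expected difference is zero.

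In a small group of 50 (assumed), a 60/40 split or worse has probability 0.20 under a binomial model, or 0.18 with a fixed 254/254 supply. The cost is slight: relative efficiency is 4 x 0.6 x 0.4 = 0.96. With SD 2, the standard error is 2 x √(1/25 + 1/25) = 0.566 at 25/25 and 2 x √(1/20 + 1/30) = 0.577 at 20/30, about 2% more.

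**5. The 127 per cell.** This needs a 50/50 preference split, which randomization does not set. At 70/30 the cells per method are about 178 and 76; at 90/10, about 229 and 25. Power for the preference main effect falls from 0.80 to 0.73 and 0.39. Stratified allocation would not change these cell sizes.

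**6. What a table of assignment by preference could show.** At a 50/50 preference split, s = 20% gives a gap of 20 points, well outside the chance range of ±8.7. At s = 10% the gap of 10 points is only just outside. Such a table is a useful check but cannot clear the process.

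**The case against.** The strongest reply is that much of this rests on silence. Several stronger readings are tempting, and the documents do not support them.

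- **One pooled, unordered supply.** A reader might infer this from the 50% rule. The text leaves order and packing by hospital unspecified; it does not say that they are absent.
- **The person who hears the preference hands over the envelope.** Identical role lists make this likely, but Section III never says so.
- **Hospital and preference are left unbalanced.** Allocation at 1:1 balances both in expectation, and the models already contain Preference and physician within hospital. The accurate statement is that balance is not protected.
- **Preference may be recorded after the slip is seen.** Section VII places it in a list of variables "retrospectively collected from EPIC or recorded during the surgery on the OR Worksheet". That is a general header, also covering items such as date of birth, and it describes abstraction. Section III requires documentation before assignment. It simply names no form.

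Two practical objections also stand. Separate series by preference require the handler to know the preference. And Version 11 is dated 3/15/2019 with enrollment ending May 31, 2019: 77 of 1,095 days, about 7% of the enrollment window, so new envelopes reach few women.

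The concealment gap survives all of this. A seal alone does not stop a second envelope from being opened, and adjusting for which method a woman prefers does not adjust for how strongly she prefers it.

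**Conclusion.** The point holds as a weakness in concealment and traceability. On the stated procedure, re-drawing toward a stated wish is neither prevented nor detectable in the individual case, and the planned model would not remove selection on strength of preference. Nothing in the documents indicates that it happened, and a reader should not infer that the result is biased by any particular amount; the size and even the sign depend on quantities the plan does not give.

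Missing stratification is a minor part: about a 2% larger standard error at a 60/40 split, with power for Method staying near 0.80. It would not secure 127 women per cell. The conclusion assumes that the safeguards not stated are also not in place under some unpublished procedure. If they are, describing them and showing the log would settle the matter.

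**What to change.** For the remaining enrollment, amend Section III as follows:

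- Use sequentially numbered, opaque envelopes, filled from a computer-generated list in randomly varying block sizes by someone who does not enroll.
- Keep separate series by hospital, and by stated preference if practical.
- Before opening, write the study number, stated preference, date and time on the next envelope in the series.
- Log every envelope in order, including any spoiled or unused.

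Before the final analysis, for all women enrolled:

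- Reconcile envelopes prepared, used and left over, by method, with the women enrolled. Where records do not allow this, say so in the report.
- Report assignment by stated preference and by hospital.
- Take Preference from the pre-assignment record that Section III already requires, and name that record.

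The cost is an amendment, re-packing of unused envelopes and slightly more handling. Re-packing protects only women not yet enrolled; the reconciliation and the table cover the whole trial and bear most on what it may conclude. The models and the target of 508 need not change.
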